### 10.2 Documentation and Reporting of Serious Adverse Events

SAEs will be documented and reported in accordance with ICH Good Clinical Practice (GCP) guidelines [32]. SAE reporting procedures for investigator initiated studies are as follows:

The Investigator must report all SAEs to the Human Research Ethics Committee Bellberry Ltd firstly by telephone and then via fax on an SAE form within 24 hours of learning of the event. Any serious event that occurs at any time over the duration of the study, regardless of whether or not the subject has undergone any study-related procedures must be reported to Bellberry Ltd.

Information on SAEs will be recorded on an SAE form. Blank copies are included in the study Investigator's File.

SAE forms should be directed to:

Bellberry Ltd

[name]

[name]

[contact] [contact]

Email: [contact]

The Investigator should follow up the event until resolution or stabilization of the condition. Follow-up reports (as many as required) should be completed and emailed following the same procedure above.

A final report is required in any case once the condition is resolved or stabilized and no more information about the event is expected. The final report should be completed and faxed following the same procedures above.

For deaths that occur following a Subject's enrolment into the study a Record of Death CRF as well as an autopsy report (when/if available) must be submitted to Bellberry Ltd. The Investigator must keep a copy of all documentation related to the event in the site's study files.

By participating in this study the Investigator agrees to submit reports of serious adverse events according to the timeline and method outlined in the protocol. In addition, the Investigator agrees to submit annual reports to his/her IRB/IEC as appropriate. The Investigator also agrees to provide Bellberry Ltd with a summary report within 30 days and full report within 60 days of completion of the Investigator's participation in the study.

# 10.3 Device-Related Observations (DROs)

A device-related observation (DRO) is defined as any malfunction, failure to operate as defined by the Instructions for Use, technical problems, or operator error associated with use of the device. For each DRO, Investigators are to report the following to Bellberry Ltd.:

- Date and time of DRO;
- Description of DRO;
- Serial number of the device with a complication;
- Clinical consequences, if any (to be reported on an AE form);
- Whether the device was replaced, and the serial number of the replacement;
- Whether or not the procedure could be completed.

### 11: STATISICAL CONSIDERATIONS AND DATA ANALYSIS

# 11.1 Sample Size and Statistical Power

The purpose of this study is feasibility testing to provide insights to develop a RCT. As such, a sample size of N=40, with 20 participants in each of the 2 population samples has been chosen. As we expect an attrition rate of 20%, we will initially recruit 50 subjects.

### 11.2 Statistical Methods

An initial descriptive analysis will be completed on the baseline measures of movement to determine mean scores, ranges and standard deviations of each sample group. This analysis will be repeated at later time points. Wilcoxon Signed Ranked Tests will be completed to determine if participant movement significantly changes following an intervention: One each for Baseline and Intervention. A repeated measures ANOVA will then be completed on all post trial data for the 2 separate groups to determine movement changes in the post-trial period.

Bivariate correlational analyses through the Pearson product-moment coefficient, will be undertaken to determine if there is a relationship between movement and "pain on movement" using data collected at each time point. This potential relationship will be mapped to assess any temporal influences.

Similarly, correlational analyses will be conducted to determine if there is a relationship between daily activity and ODI scores, using data collected at each of the four total time points. This potential relationship will also be mapped over time to determine if there are any temporal effects following initial treatment.

All findings with a p-value < 0.05 will be deemed significant.

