# 8.4 Methodology

The following tasks will be conducted on the recruitment day (Day 0) for all subjects, and will be recorded in each subject's respective source documents and case report forms (CRFs):

- 1. Assessment of eligibility against inclusion and exclusion criteria
- 2. An explanation of study procedures.
- 3. Provision and obtainment of written informed consent.
- 4. Obtainment of demographic information and medical history.
- 5. Booking of Day 1 and Day 2 (based on convenience).

The main study will be conducted over 2 consecutive days for each subject.

Participants will be asked to complete each of the following - 30 minutes prior to their appointment on Day 1; the Oswestry Disability Index (ODI), a Numeric Rating Scale for Pain (NRS Pain), the Roland Morris Disability Questionnaire, and a Low Back Pain Classifier.

Both subject groups will then have a "start interview" on their allocated baseline assessment day (Day 1). This will include fitting of the ViMove movement and EMG sensors, as well as a ViMove live "pain on movement" assessment. This session will take approximately 20-30 minutes. Whilst wearing the ViMove sensors, subjects will then leave the clinic and conduct normal daily activities for a predetermined monitoring period. No ThermaCare HeatWraps are worn on Day 1. This allows a baseline assessment and allows any placebo effects from the sensors to be discounted. At the end of the monitoring session, subjects will return to the clinic to have an "end-of-day" interview. Participants will complete a Patient Global Impression of Change scale (PGIC), a repeat NRS, and will have another live ViMove assessment. Movement sensors will then be removed, and the subject will be reimbursed for that day.

The intervention day (Day 2) will have the same procedure as Day 1 (baseline), with the only difference being the additional application of ThermaCare HeatWraps during the "start interview". ThermaCare will only be applied after the live assessment, so will not be worn at the same time as the EMG sensors. Subjects will continue to wear the HeatWrap and ViMove sensors during the 8-hour daily activity monitoring period, with the wrap and sensors being removed during the end-of-day interview, prior to the end-of-day live assessment. The subject will then be reimbursed for Day 2. A schedule of events can be seen in Table 1, and a summary of the procedure can be seen in Figure 1.

Table 1. Schedule of Events

[figure not shown]

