Tuble 1: Senedale of Events	Visit 1*	Visit 2*	Visit 3	Visit 4	Visit 5
		Baseline	Baseline	Intervention	
	(Day 0) Enrol-	Baseline Start	End of	Start	Intervention End of Day
		Interview		Interview	Interview
	ment		Day	interview	interview
		(within 3 weeks of	Interview		
		Visit 1)			
Eligibility	х				
Informed consent	х				
Demographics & Medical History	Х				
Enrolment and scheduling	Х				
Questionnaires		x		x	х
ViMove application		х		х	
ViMove in clinic assessment		х	Х	х	Х
ViMove monitoring assessment		х		х	
ViMove removal			Х		Х
ThermaCare application				х	
ThermaCare removal					Х
Adverse Events		х	Х	х	Х
Changes in medications		х		х	
Study Termination					х

\*Baseline may occur on the same day as Visit 1 (i.e. enrolment).

Subjects who withdraw from the study after providing informed consent are referred to as "dropouts" or premature withdrawals. The drop-out rate will be summarized. If the patient has provided a whole set of Day 1 data, this will be included in the study.

We expect 6-months will be required from first participant enrolment to the last participant visit. A further 3-months will be required for analysis and write-up.

Figure 1. Summarized Procedure

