### 13: STUDY OUTCOMES AND SIGNIFICANCE

# **13.1 Primary Endpoints**

- 1. Collection of movement and erector spinae muscle activity data in all participants.
- 2. Change over time in range of motion (ROM) in any one plane of movement compared to preintervention ROM.
- 3. A change over time in Flexion-Relaxation response in those subjects where abnormal EMG activity in flexion during baseline assessment is detected.
- 4. A change over time in maximum pain during movement score (1-10 as recorded during the inclinic ViMove assessment) for any one plane of movement.

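### Section 11.2 tests movement change separately on the no-wrap day and the wrap day and never compares the two changes, so heat cannot be separated from drift common to both days

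*Combined protocol and SAP*

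**What the plan says.** Section 8.4 describes two consecutive days. On Day 1 participants wear sensors only, and the stated purpose is: "This allows a baseline assessment and allows any placebo effects from the sensors to be discounted". Day 2 "will have the same procedure as Day 1 (baseline), with the only difference being the additional application of ThermaCare HeatWraps". The description of the global impression scale in Section 8.5.4 confirms the labels: Baseline is Day 1 and Intervention is Day 2. In Table 1 the row "ViMove in clinic assessment" is marked at Visits 2 and 3 (start and end of Day 1) and at Visits 4 and 5 (start and end of Day 2).

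For movement, Section 11.2 plans: "Wilcoxon Signed Ranked Tests will be completed to determine if participant movement significantly changes following an intervention: One each for Baseline and Intervention". It does not name the visits, but Table 1 implies start against end within each day. It then adds: "A repeated measures ANOVA will then be completed on all post trial data for the 2 separate groups". The rest of Section 11.2 is descriptive summaries and Pearson correlations, under one rule: "All findings with a p-value < 0.05 will be deemed significant".

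Section 13.1 lists as a primary endpoint: "Change over time in range of motion (ROM) in any one plane of movement compared to preintervention ROM". On dropouts, Section 8.4 says: "If the patient has provided a whole set of Day 1 data, this will be included in the study".

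**The concern.** Discounting what happens without the wrap requires setting the Day 2 change against the Day 1 change. The design collects the data for that, but the stated analysis gives each day its own p-value and stops there. Time of day, repeated testing and hours of sensor wear act on both days. If they move range of motion, the Day 2 test responds to them as well as to heat.

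The pair of p-values can mislead in two ways. Day 2 significant with Day 1 not significant can arise from drift alone, because a difference in significance is not a test of a difference. Both days significant can hide a real heat effect. The two tests may also cover different people, since participants with only a full Day 1 data set are kept.

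The study is a feasibility pilot (Sections 8.2 and 11.1), which limits the stakes. But the aims in Section 3.1 are efficacy, range-of-motion change is a primary endpoint, and the results are meant to guide a randomised trial. Planning that trial needs an estimate of the Day 2 minus Day 1 difference and its spread.

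**Working it through.** **Figures in the plan.** The only sample size arithmetic is the attrition allowance: 40 / (1 − 0.20) = 50, which reproduces. No SD, effect size, drift, correlation or power is given.

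**Inputs.** From the plan: 20 per group and p < 0.05 (taken as two-sided). Assumed: normal within-day changes with SD 1; the same mean drift on both days; correlation ρ between the two daily changes of 0 or 0.5. The exact signed-rank test at n = 20 rejects when the smaller rank sum is at most 52 (size 0.048). Rates are from simulation.

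**Step 1: no heat effect, equal drift.** Let p be the chance that one day's test is significant. At ρ = 0, the chance of *Day 2 only* is p(1 − p) and of *both days* is p². At 0.5 SD drift p ≈ 0.54, so 0.54 × 0.46 = 0.25 and 0.54² = 0.29, which agrees with the simulation.

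| Drift (SD) | Day 2 only, ρ = 0 / 0.5 | Direct contrast |
|---|---|---|
| 0.2 | 11% / 9% | 5% |
| 0.3 | 18% / 13% | 5% |
| 0.4 | 24% / 17% | 5% |
| 0.5 | 25% / 17% | 5% |
| 0.8 | 8% / 6% | 5% |

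The pattern becomes rarer at 0.8 SD because both days are then significant in 83% / 85% of trials, which would alert a reader to drift.

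**Step 2: the opposite failure.** At 0.5 SD drift, both days are significant in 30% / 37% of trials with no heat effect, and in about 54% with a real 0.5 SD heat effect. That pattern separates the two situations poorly.

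**Step 3: the direct contrast.** D = (Visit 5 − Visit 4) − (Visit 3 − Visit 2). Its SD is √(2(1 − ρ)): 1.41 at ρ = 0 and 1.00 at ρ = 0.5. A 0.5 SD heat effect is therefore 0.5 / 1.41 = 0.35 or 0.5 / 1.00 = 0.50 in units of D's SD, giving power of about 31% or 54%. A single-day test has about 54% for the same effect with no drift. The mean half-width of the 95% Hodges-Lehmann interval for D is about 0.67 SD (ρ = 0) or 0.48 SD (ρ = 0.5).

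**Step 4: the ANOVA read as Visit 5 against Visit 3.** Visit values were simulated with person SD 1.5, day SD 0 / 0.5 / 1, visit noise giving a within-day change SD of 1, and drift of 0.3 SD. The SD of Visit 5 − Visit 3 is √(1 + 2 × day SD²) = 1.00 / 1.22 / 1.73.

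| | Day SD 0 | Day SD 0.5 | Day SD 1 |
|---|---|---|---|
| Error, common drift only | 5% | 5% | 5% |
| Error, Day 2 starts 0.3 SD higher without heat | 24% | 18% | 11% |
| Power at 0.5 SD, no overnight shift | 57% | 41% | 23% |

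In the same model D keeps about 5% error throughout and has about 31% power.

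**The case against.** The strongest defence is the ANOVA. If its data are the two end-of-day assessments, it compares the days and holds about 5% error under common drift, which is the problem raised here. With little day-to-day variation it is also more powerful than D. This stands as a partial remedy on one reading. But Section 11.2 names no visits, factors or day-by-time term, and refers to a post-trial period although Table 1 has no visit after Visit 5. It cannot be credited as a stated contrast, and on that reading it ignores each day's starting value.

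Second, the plan never says that Day 2 significant with Day 1 not will be read as a heat effect. That is so: the 9% to 25% is the frequency of a misleading pattern, not a planned type I error. The plan offers no other rule for reading the two p-values together.

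Third, the 5% for D depends on equal drift. Section 8.4 itself describes further differences between the days. On Day 1 the sensors come off after the end-of-day assessment, whereas on Day 2 wrap and sensors are described as removed before it. Eight hours of monitoring is stated only for Day 2. With assumed drifts of 0.3 SD on Day 1 and 0.6 SD on Day 2 and no heat effect, D rejects in 14% / 24% of trials (ρ = 0 / 0.5). The planned pair shows *Day 2 only* in 54% / 49%, so D is still better, but the condition must be stated.

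Fourth, the endpoint may be met in any single plane, and Section 4 lists four movements. Independent tests of D in four measures would give 1 − (1 − 0.048)⁴ ≈ 18% chance of at least one rejection. This is a separate problem that affects the planned tests equally.

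**Conclusion.** The concern holds and should be fixed. No section states a comparison of the Day 2 change with the Day 1 change, although Section 8.4 sets up Day 1 for that purpose. The size depends on assumed drift and correlation. At 0.2 to 0.5 SD of equal drift and 20 participants per group, a Day 2 only result arises with no heat effect in about 9% to 25% of trials; the contrast holds about 5% as long as drift is the same on both days. The omission lies in the analysis plan, not in the data, and the pilot status keeps it below a critical fault.

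**What to change.** - In Section 11.2, make D = (Visit 5 − Visit 4) − (Visit 3 − Visit 2) the main movement analysis, in each group separately and in participants with both days. Use a Wilcoxon signed-rank test and a Hodges-Lehmann estimate with 95% CI, and name the plane or planes to which it applies.
- Keep the two single-day tests as descriptive and name their visits.
- Define the ANOVA's visits and factors or remove it. If it is defined as day (1, 2) by time (start, end) over Visits 2 to 5 within each group, its day-by-time interaction is the parametric form of D.
- Section 11.2 plans no test of change for pain on movement or flexion-relaxation. If these are to be tested, use the same contrast.
- Reconcile the Section 8.4 wording on sensor removal and monitoring length for the two days.
- State the limits: with fixed order and an unblinded wrap, D removes only drift common to both days. It does not remove order, learning, recovery or wrap-placebo effects, or effects of sensor refitting or unequal monitoring time.

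This costs wording only: no new data, visits or participants. The real price is precision: at a 0.5 SD effect D has about 31% to 54% power, and its 95% CI half-width is about 0.67 to 0.48 SD (correlation 0 to 0.5). That is acceptable for a pilot that reports estimates rather than claiming efficacy.

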# 3.2 Hypotheses

The Hypotheses for each aim are as follows:

- 1. ThermaCare HeatWraps are an effective intervention for people with low back pain as it:
  - a. Decreases pain during movement.
  - b. Improves muscle relaxation.
  - c. Increases flexibility (range of movement).
- 2. ThermaCare HeatWraps are an effective intervention for people actively involved in sport as it:
  - a. Improves muscle relaxation.
  - b. Increases flexibility.
  - c. Delays or reduces the incidence of pain as defined by an increase in existing pain or the occurrence of new pain.

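### Section 11.2 specifies analyses of change for movement only, so neither primary endpoint 4 and hypothesis 1a (pain on movement) nor primary endpoint 3 (Flexion-Relaxation) has a prespecified analysis of change.

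*Combined protocol and SAP*

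**What the plan says.** Section 13.1, repeated in the Protocol Summary, lists four primary endpoints. The first is collection of data and the other three are changes. Endpoint 2 is a change in range of motion. Endpoint 3 is "A change over time in Flexion-Relaxation response in those subjects" whose baseline EMG in flexion is abnormal. Endpoint 4 is "A change over time in maximum pain during movement score", for any one plane. Section 3.2 puts a directional claim first for the back-pain group: "Decreases pain during movement". Muscle relaxation is hypothesis 1b for that group and 2a for the sport group.

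Section 11.2 then sets out the analyses:
- Descriptive: "An initial descriptive analysis will be completed on the baseline measures of movement to determine mean scores, ranges and standard deviations of each sample group", repeated at later time points.
- Paired tests: "Wilcoxon Signed Ranked Tests will be completed to determine if participant movement significantly changes following an intervention: One each for Baseline and Intervention".
- Repeated measures ANOVA: "to determine movement changes in the post-trial period".
- Correlation: "Bivariate correlational analyses through the Pearson product-moment coefficient, will be undertaken to determine if there is a relationship between movement and" pain on movement at each time point. It is this relationship that is then mapped over time.
- A second correlation, between daily activity and ODI.

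A p-value below 0.05 counts as significant throughout.

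**The concern.** Three primary endpoints are changes, and section 11.2 provides an analysis of change for only one of them, range of motion. The pain score has one stated use, a correlation with movement, and that answers a different question from whether pain fell. Muscle activity and EMG do not appear in section 11.2 at all.

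Two things are at stake. First, the leading hypothesis for Group 1 has no planned estimate, test or summary. Sections 8.2 and 11.1 say the study is meant to guide an RCT, and for that the size and variability of the pain change are among the most useful results. Second, if the pain analysis is chosen after the data are seen, the any-one-plane wording of endpoint 4 leaves room to pick the most favourable plane.

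**Working it through.** **The plan's own figure.** The only sample-size arithmetic is the recruitment target: 40 / (1 − 0.20) = 50, which reproduces. Section 11.1 gives no power, effect size or SD, so there is no power figure to check. The point does not depend on this.

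**Matching analyses to endpoints.**

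| Analysis in 11.2 | Range of motion (endpoint 2) | Flexion-Relaxation (endpoint 3) | Pain on movement (endpoint 4, hypothesis 1a) |
|---|---|---|---|
| Descriptive summary | yes | no | no |
| Wilcoxon signed-rank | yes | no | no |
| Repeated measures ANOVA | yes | no | no |
| Pearson correlation | one side | no | other side |
| Activity–ODI correlation | no | no | no |

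The word movement cannot be stretched to cover the pain score or EMG. Section 8.5.1 lists movement data, surface muscle activity and pain on movement as separate measures, and section 11.2 itself puts movement and pain on movement on opposite sides of the correlation.

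**Can the correlation show a fall in pain?** With x for movement and y for pain,

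r = Σ(xᵢ − x̄)(yᵢ − ȳ) / √[Σ(xᵢ − x̄)² · Σ(yᵢ − ȳ)²].

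Replace each yᵢ by yᵢ − c. The mean becomes ȳ − c, every deviation yᵢ − ȳ is unchanged, and so is r. In one simulated sample of 20, lowering every score by 0, 1 and 2 points gave mean pain of 4.93, 3.93 and 2.93, with r = −0.4698 each time.

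On a bounded whole-number 0–10 scale the invariance is only approximate. In 3,000 simulated trials of 20 subjects with an assumed true pain–movement correlation, mean pain fell from 4.5 to 3.5 to 2.6. Mean r stayed at −0.53, and the share of significant correlations stayed at 73–74%. Mapping r over the visits therefore does not track the level of pain.

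**What a direct analysis could deliver.** For each subject let D = (Visit 5 − Visit 4) − (Visit 3 − Visit 2). If each day's change has SD σ and the two changes correlate at ρ, then SD(D) = σ√[2(1 − ρ)].

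Inputs: n = 20 per group (section 11.1); significance level 0.05 (section 11.2), taken as two-sided because the plan does not say; net fall of 1 point, and σ and ρ, all assumed. Power is by simulation of the signed-rank test with normal changes. The approximate 95% CI half-width is 2.093 × SD(D)/√20.

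| σ | ρ | SD(D) | Power | CI half-width (points) |
|---|---|---|---|---|
| 1.5 | 0 | 1.5 × 1.414 = 2.12 | about 50% | 0.99 |
| 1.5 | 0.5 | 1.5 × 1 = 1.50 | about 79% | 0.70 |
| 2.0 | 0 | 2.0 × 1.414 = 2.83 | about 31% | 1.32 |
| 2.0 | 0.5 | 2.0 × 1 = 2.00 | about 55% | 0.94 |

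**The case against.** The best defence is that this is a feasibility study. Sections 8.2 and 11.1 say so, 40 subjects were not chosen for power, and the pain scores will be collected whatever section 11.2 says, so an analysis can be added later. That excuses the missing power calculation and shows that no data would be lost. It does not excuse a declared primary endpoint and a directional hypothesis with no matching analysis, in a protocol that states efficacy aims (section 3.1) and a significance threshold.

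Other parts of the defence stand, and they limit what can be claimed:

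- A reader might infer that hypothesis 1a will be judged from the correlations, or that the report will contain no figure for pain. The documents support neither. Section 11.2 gives the correlations the purpose of describing a relationship, and section 13.3 expects information on changes in pain. What is missing is a prespecified method.
- A reader might infer that section 11.2 tests nothing but movement. The 0.05 threshold also applies to the correlations, so the statement is exact only for tests of change.
- It is tempting to set the correlation's rate of significant results against the power of a signed-rank test. The two test different hypotheses, and the correlation's rate depends on the true pain–movement correlation, which the documents do not give: simulated at n = 20, it is about 5% at a true correlation of 0 and 64% at −0.5. The invariance argument needs no such comparison.
- It is also tempting to quote power for a single day's change as if it applied to the contrast between days. That holds only if the two daily changes correlate at about 0.5.

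**Conclusion.** The point holds as a gap in the analysis plan. Section 11.2 as written provides no test, estimate or summary of change for primary endpoint 4 and hypothesis 1a, and none for primary endpoint 3. This follows from the text and from an algebraic property of the correlation coefficient, and rests on no assumed number.

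The assumed quantities bear only on how precise the remedy would be. The single-day SD, the correlation between days and the 1-point fall are not in the documents, so the figures of roughly 31% to 79% show a range and predict nothing. The gap should be closed before the data are analysed. It does not mean that the data collection is deficient or that the sample size must change.

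**What to change.** Add one paragraph to section 11.2:

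1. **Pain on movement.** For each subject, calculate the Visit 4 to 5 change minus the Visit 2 to 3 change in the maximum pain-on-movement score. Analyse it by Wilcoxon signed-rank with an estimate and 95% CI. Group 1 is the main analysis for hypothesis 1a; report Group 2 separately. The contrast uses Day 1, when no HeatWrap is worn, as the comparison that section 8.4 intends.
2. **One summary score.** State openly that the any-one-plane wording of endpoint 4 is replaced by a single prespecified summary: the highest score over the movements, taken by the same rule at every visit. Alternatively, analyse each plane with a multiplicity adjustment. Reconcile the 1–10 range in endpoint 4 with the 0–10 scale in section 8.5.2.
3. **Flexion-Relaxation.** Apply the same contrast, by group, in the subjects with abnormal baseline EMG in flexion, as endpoint 3 defines. If the subset is small, report it descriptively with a CI.
4. **Correlations.** Say that they describe a relationship and are not evidence of a change in pain.

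Cost: no new data and no extra subjects, because Table 1 schedules the in-clinic assessment at Visits 2, 3, 4 and 5 and section 8.5.2 has pain scored at each movement. The drawbacks are the possible imprecision of the day contrast at n = 20, which is why the estimate and interval should lead the report rather than the p-value, and an explicit change to the wording of endpoint 4.

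### Section 11.2 plans a repeated measures ANOVA of movement change in a post-trial period, but only one live assessment follows the wrap, so the analysis needs to be defined on the visits that exist

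*Combined protocol and SAP*

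**What the plan says.** On the ANOVA, section 11.2 reads: "A repeated measures ANOVA will then be completed on all post trial data for the 2 separate groups to determine movement changes". The rest of that sentence places the changes in a post-trial period. The sentence before it plans Wilcoxon signed-rank tests of movement, one for the baseline day and one for the intervention day. A later paragraph of 11.2, on the correlation between daily activity and ODI, aims to "determine if there are any temporal effects following initial treatment".

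Section 8.4 sets the schedule: "The main study will be conducted over 2 consecutive days for each subject". On the first day, "No ThermaCare HeatWraps are worn on Day 1". On the second, "ThermaCare will only be applied after the live assessment, so will not be worn at the same time as the EMG sensors". The wrap is worn through the 8-hour monitoring period, "with the wrap and sensors being removed during the end-of-day interview, prior to the end-of-day live assessment". Table 1 marks the in-clinic ViMove assessment at Visits 2, 3, 4 and 5, and marks "Study Termination" at Visit 5. It has no later column.

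**The concern.** A repeated measures analysis of change within a period needs at least two measurements per subject in that period. The schedule gives one after the wrap and none after the trial. An analyst following 11.2 would have to decide which visits count as post-trial data, possibly after seeing them, and the choice changes the question being answered.

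This matters because range of motion change is a primary endpoint (section 13.1). Each Wilcoxon test appears to be confined to its own day. The ANOVA is then the only planned movement test that could set the wrap day against the no-wrap day, and section 8.4 includes Day 1 so that placebo effects of the sensors can be discounted. A result reported under the present wording could also be taken as a time course after treatment, for which there are no data.

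**Working it through.** **The plan's own figure.** Section 11.1 wants 40 subjects, 20 per group, at 20% attrition: 40 / (1 − 0.20) = 50, as stated. The point here does not depend on this figure. It only supplies n = 20 per group below.

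**Live assessments (section 8.4 and Table 1).**

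| Visit | Occasion | Wrap status at the live assessment |
|---|---|---|
| 2 | Day 1 start | no wrap that day |
| 3 | Day 1 end | no wrap that day |
| 4 | Day 2 start | before application |
| 5 | Day 2 end | after removal; study ends |

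After the wrap: 1 occasion. After study termination: 0.

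**Other possible sources of post-treatment movement data.** Day 2 monitoring is recorded while the wrap is on. Section 9.1 mentions follow-up sessions, but neither 8.4 nor Table 1 schedules one beyond Day 2. Adverse event follow-up (section 10.1) yields no movement data. Figure 1 is not reproduced in the text, but 8.4 describes it as a summary of this same procedure.

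**Degrees of freedom.** With k occasions and n subjects in a group, time df = k − 1 and error df = (n − 1)(k − 1). At n = 20:

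- Literal reading, Visit 5 only: k = 1, time df = 0, error df = 19 × 0 = 0. Nothing can be estimated within subjects.
- End-of-day reading, Visits 3 and 5: k = 2, time df = 1, error df = 19 × 1 = 19.
- All four assessments: k = 4, time df = 3, error df = 19 × 3 = 57. Arranged as day (no wrap, wrap) by session (start, end), the 3 df split into day, session and day-by-session, 1 df each, with 19 error df each (3 × 19 = 57).

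**What each contrast measures.** Write V2 to V5 for a subject's values. The end-of-day reading uses V5 − V3. The day-by-session interaction is (V5 − V4) − (V3 − V2), which rearranges to (V5 − V3) − (V4 − V2). The two therefore differ by V4 − V2, the difference between the two mornings, which arises before any wrap is applied. The end-of-day contrast carries that difference; the interaction removes it. A single four-level time factor would mix both with the ordinary change over a day, and so would not isolate the wrap.

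**The case against.** The best defence is that post-trial means post-session. Section 11.2 has just treated each day as its own before-and-after comparison, so the data meant may be the end-of-day assessments of both days. That ANOVA can be run, and comparing Visit 5 with Visit 3 is informative about the wrap. This stands: a reader might infer from the zero degrees of freedom that the planned ANOVA is impossible, or that the study cannot assess the wrap's effect on movement, and the documents support neither. What does not stand is that this reading settles the matter. The text does not state it, two end-of-day values are not a post-trial period, and the start-of-day values are left unused.

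Three further limits are fair:

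- The phrase on temporal effects belongs to the activity-ODI correlation, not to the ANOVA, so the degrees-of-freedom argument does not apply to it. It has a separate problem: there is one application and no visit after the day of wear.
- Day 2 monitoring includes range-of-motion measures during wear. It may bear on whether a change develops under the wrap, though not on what happens after removal.
- No aim, objective or endpoint claims persistence. Objective 3 concerns the state after 8 hours of use and objective 4 a pre-post comparison. A reader might fear that the later randomised trial would take over a follow-up assumption from this pilot, but the documents mention none, so that harm is conjecture.

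**Conclusion.** The point holds as an error in the wording of the analysis. As written, the ANOVA targets change in a period with one post-wrap assessment and none after termination, which gives 0 within-subject df. On the most workable alternative reading it has 1 and 19 df per group and compares the wrap day with the no-wrap day, but it does not match its stated purpose and discards half of the live assessments (2 of 4).

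The df assume 20 subjects with complete data per group. Reading the interaction as the effect of the wrap assumes that, without it, movement would change from start to end of day equally on both days. The order is fixed, with the wrap always on Day 2, so the data cannot test this. The conclusion is structural and rests on no effect size, standard deviation or power, none of which the documents give. It should be corrected before analysis, but it does not call the design of the pilot into question.

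**What to change.** In section 11.2:

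1. Delete the reference to the post-trial period from the ANOVA sentence.
2. State that, within each group, the repeated measures ANOVA uses the four live assessments (Visits 2, 3, 4 and 5) with within-subject factors day (no wrap, wrap) and session (start, end), and that the day-by-session interaction is the test of the wrap.
3. State that conclusions on movement apply to the state immediately after about 8 hours of wear, with no statement on persistence.
4. In the activity-ODI paragraph, limit the mapping over time to the scheduled assessments and remove the suggestion of effects followed up after treatment.

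The cost is wording only: no new visit, measurement or subject. The study gives up a claim that its schedule cannot support.
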